## **18.0 Provisions to Monitor the Data to Ensure the Safety of Subjects\***

N/A; The probability of harm or discomfort anticipated in this study are no greater than those encountered in daily life or during the performance of routine physical or psychological tests.

## **19.0 Provisions to Protect the Privacy Interests of Subjects**

Subject identifiers will only be included in the master list linking subjects to their Study ID (Appendix C). Subjects in the Control Group will receive standard care, including usual privacy standards. Subjects in the Exercise Group will interact with the same trainer throughout the study, so that rapport can be developed, putting the subject at ease. All exercise activities will be individually tailored to the subject's needs.

To access data from the subjects' electronic medical records, a request will be sent to Information Systems (IS). Once received, identifiers will be replaced with Study ID number.

## **20.0 Compensation for Research-Related Injury**

N/A; The study does not involve more than minimal risk.

## **21.0 Economic Burden to Subjects**

Subjects in the Exercise Group may incur costs associated with once weekly travel to Maple Tree Cancer Alliance. No other study-related costs to subjects are expected.

## **22.0 Consent Process**

All patients will be fully informed about the study and will have time to ask questions and consider their decision to participate. A research intern for Maple Tree Cancer Alliance, [name], will provide a written informed consent form to eligible patients and meet with them in person to discuss the study in a private room at the Kettering Cancer Center or the Soin Cancer Center. Patients will be provided with the informed consent form and the intern will go through the information in the form with the patient. Patients will be invited to take the form home and talk with family and friends before deciding if they would like to participate. If patients wish to take some time to make the decision, they may inform the intern about their decision to participate or decline participation via phone.

## **23.0 Process to Document Consent in Writing**

Participants will document consent to participate using the consent form in Appendix D.

## **24.0 Setting**

Subjects will be recruited from patient populations at Kettering and Soin Cancer Centers and identified through presentation at breast tumor conferences held at these facilities (see Section 13.0). For the Exercise Group, exercise will occur at Maple Tree Cancer

PROTOCOL TITLE: Randomized, Controlled Trial of an Individualized Exercise Oncology Program for Newly Diagnosed Breast Cancer Patients

Alliance as described in Section 5.0. For the Control Group, all research activities will entail usual care at standard treatment locations. Treatment decisions for both groups are independent of study participation.

## **25.0 Resources Available**

The study team has adequate resources to execute this study in a timely manner.

**Appendix A: Randomization Scheme using Block Size of 10**

Subject	Study Group Assignment
1	Control
2	Exercise
3	Exercise
4	Exercise
5	Control
6	Control
7	Control
8	Control
9	Exercise
10	Exercise
11	Exercise
12	Control
13	Control
14	Control
15	Exercise
16	Exercise
17	Control
18	Control
19	Exercise
20	Exercise
21	Control
22	Exercise
23	Exercise
24	Control
25	Exercise
26	Exercise
27	Control
28	Control
29	Exercise
30	Control
31	Exercise
32	Exercise
33	Control
34	Control
35	Exercise
36	Control
37	Control
38	Exercise
39	Exercise
40	Control
41	Exercise
42	Control

PROTOCOL TITLE: Randomized, Controlled Trial of an Individualized Exercise Oncology Program for Newly Diagnosed Breast Cancer Patients

43	Exercise
44	Exercise
45	Exercise
46	Control
47	Control
48	Exercise
49	Control
50	Control
51	Exercise
52	Exercise
53	Exercise
54	Control
55	Control
56	Control
57	Control
58	Exercise
59	Exercise
60	Control
61	Control
62	Control
63	Exercise
64	Exercise
65	Control
66	Exercise
67	Control
68	Exercise
69	Exercise
70	Control

PROTOCOL TITLE: Randomized, Controlled Trial of an Individualized Exercise Oncology Program for Newly Diagnosed Breast Cancer Patients

Appendix B

**Randomized, Controlled Trial of an Individualized Exercise Oncology Program**

Determination of eligibility (to be completed by Maple Tree Cancer Alliance research intern)

Patient Name \_\_\_\_\_

Is the patient female, as determined from electronic medical record?	 Yes  No (Ineligible)
Does the patient have an initial stage 1 or 2 breast cancer diagnosis within the past 12 weeks, determined from electronic medical record?	 Yes  No (Ineligible)
Is the patient age 30-80, determined from electronic medical record?	 Yes  No (Ineligible)
Does the patient have documented physician clearance to participate in exercise?	 Yes  No (Ineligible)
Has the patient participated in supervised physical exercise within the past 6 months?	 Yes (Ineligible)  No
Is the patient currently pregnant or planning to become pregnant?	 Yes (Ineligible)  No
Does the patient speak and read English fluently?	 Yes  No (Ineligible)
Is the patient able to make their own medical decisions and to follow verbal instructions?	 Yes  No (Ineligible)

PROTOCOL TITLE: Randomized, Controlled Trial of an Individualized Exercise Oncology Program for Newly Diagnosed Breast Cancer Patients

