## 1.0 Study Summary

Study Title	Randomized, Controlled Trial of an Individualized Exercise Oncology Program for Newly Diagnosed Breast Cancer Patients
Study Design	Randomized, controlled trial
Primary Objective	The primary objective is to test the effect of an individualized exercise oncology program on healthcare utilization, 30-day hospital readmission, pain, and cancer treatment tolerance.
Secondary Objective(s)	The secondary objective is to examine the feasibility of an individualized exercise oncology program via adherence and attrition rates.
Research Intervention(s)/Investigational Agent(s)	Individualized Exercise Oncology Program
IND/IDE #	N/A
Study Population	Female patients age 18+ newly diagnosed with stage 0, 1 or 2 breast cancer.
Sample Size	70
Study Duration for individual participants	12 weeks
Study Specific Abbreviations/Definitions	N/A

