## 2.0 Objectives\*

The primary objective is to test the effect of an individualized exercise oncology program on healthcare utilization, 30-day hospital readmission, pain, and cancer treatment tolerance.

H1: Among women newly diagnosed with stage 0, 1 or 2 breast cancer, those enrolled in an individualized exercise oncology program will have fewer emergency room (ER) visits, fewer hospital encounters, fewer 30-day hospital readmissions, fewer breaks in cancer treatment, less pain, and better cancer treatment tolerance than those in the control group over 3 months.

The secondary objective is to examine the feasibility of an individualized exercise oncology program via adherence and attrition rates.

H2: Among women newly diagnosed with stage 0, 1 or 2 breast cancer and enrolled in an individualized exercise oncology program, adherence to scheduled exercise sessions will average 70% or more, and program attrition will average 70% or less over 3 months.

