## **10.0 Inclusion and Exclusion Criteria\***

Patients will be selected according to the Consolidated Standard of Reporting Trials criteria. Criteria not determined via EMR are determined via the form in Appendix B. Inclusion criteria are:

- Female; determined from electronic medical record
- Initial stage 0, 1 or 2 breast cancer diagnosis within the past 12 weeks determined from electronic medical record
- Age 30-80; determined from electronic medical record
- Physician clearance to participate in exercise

Exclusion criteria are:

- Participation in supervised physical exercise within 6 months prior to study enrollment
- Currently pregnant or planning to become pregnant
- Non-English speaking
- Unable to make own medical decisions and/or to follow verbal instructions

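### The Appendix B eligibility form asks only about stage 1 or 2, so followed literally it turns away the stage 0 patients that Section 10.0 includes.

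*Combined protocol and SAP*

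**What the plan says.** Four sections define the population by stage, and they agree. The Study Summary (Section 1.0) describes it as "Female patients age 18+ newly diagnosed with stage 0, 1 or 2 breast cancer". Both hypotheses in Section 2.0 open with "Among women newly diagnosed with stage 0, 1 or 2 breast cancer". Section 6.0 invites women with a recent diagnosis of the same three stages. Section 10.0 gives the formal criterion: "Initial stage 0, 1 or 2 breast cancer diagnosis within the past 12 weeks determined from electronic medical record".

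Appendix B is the form for determining eligibility, completed by the research intern. Its stage item reads "Does the patient have an initial stage 1 or 2 breast cancer diagnosis within the past 12 weeks". The two answer boxes are yes and no, and the no box is marked ineligible. Stage 0 is not mentioned anywhere on the form.

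Section 10.0 also says what the form is for: it covers the criteria that are not determined from the electronic medical record (EMR). Section 12.0 says that only patients who meet the criteria are enrolled. Appendix C records each excluded patient with a reason, and failing the eligibility criteria is one of the reasons offered.

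**The concern.** The form and the inclusion criterion give opposite answers for the same woman. With a stage 0 diagnosis made within 12 weeks, she is eligible under Section 10.0 and ineligible on the form.

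Three things are at stake. The first is the population: a trial screened literally by the form enrols stages 1 and 2 only, while H1 and H2 are stated for stages 0 to 2. The second is the participant flow: the Appendix C log would count eligible women as not meeting the criteria, and the CONSORT report would carry that error. The third is that the loss cannot be repaired at analysis. Women turned away at screening are not in the data, and each leaves the eligibility window 12 weeks after diagnosis.

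**Working it through.** The plan states no figure that bears on this point, so the check is a comparison of texts.

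**Step 1. Stage and age, place by place.**

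| Place | Stages | Age |
|---|---|---|
| Section 1.0, Study Summary | 0, 1, 2 | 18+ |
| Section 2.0, H1 and H2 | 0, 1, 2 | not stated |
| Section 6.0, Procedures | 0, 1, 2 | 30-80 |
| Section 10.0, Inclusion criteria | 0, 1, 2 | 30-80 |
| Appendix B, form | 1, 2 | 30-80 |

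On stage, the form stands alone against four sections. On age, the summary stands alone, and the form agrees with Section 10.0.

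**Step 2. Does anything explain the difference?** The revision history lists one revision (17JAN2020), which added a recruitment method. It does not mention stage. Nothing in the text removes stage 0 from the population, and the item is complete as printed, so neither a redaction nor a reading error accounts for it.

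**Step 3. The rest of the form against Section 10.0.** Sex, age, recent supervised exercise, pregnancy and decision-making capacity correspond. Two other items do not match exactly. The form requires fluent speaking and reading of English, whereas Section 10.0 excludes only patients who do not speak English, so the form is stricter. The form also asks that physician clearance be documented, which Section 10.0 does not specify.

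**Step 4. What follows in the trial.** Section 6.0 randomizes after enrolment and consent, so a screening exclusion happens before assignment and does not depend on arm. Section 9.0 keeps enrolment open until 70 patients are in, so the exclusion does not reduce the sample size.

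**Step 5. Accrual, as illustration only.** Section 9.0 expects enrolment to take about 6 months. If a share *s* of otherwise eligible patients is stage 0, the flow is otherwise constant, and the 6 months was forecast with those patients counted, the time becomes 6 / (1 − *s*):

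- *s* = 10%: 6 / 0.90 = 6.7 months
- *s* = 30%: 6 / 0.70 = 8.6 months

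Both values of *s* are assumptions. The documents give no stage distribution and do not say how the 6 months was derived.

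**The case against.** The strongest reply is that the form does not govern stage at all. Section 10.0 confines it to criteria not read from the EMR and lists stage as an EMR item. Section 13.2 has the research coordinator identify eligible patients at tumor conferences before they are approached. On that reading, staff apply Section 10.0 from the record and the faulty line does no harm.

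This stands in part. It means that the form cannot be called the sole or controlling screening tool, and that exclusion of stage 0 is conditional on the form being followed as printed. It does not remove the conflict. The form repeats the EMR items for sex, stage and age and gives each an outcome of ineligible. Staff therefore hold two instructions, and for stage the form's printed outcome contradicts the criterion.

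The reply is also right about consequences. A reader might infer that the treatment comparison is biased or that power is lost through fewer patients. Screening precedes randomization and enrolment runs to 70, so the documents support neither. A reader might also infer that stage 0 patients were in fact turned away, or that accrual will slip by a known amount. The documents contain no screening data and no stage distribution, so neither can be concluded.

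Finally, the age difference in Section 1.0 is not a fault of the form. A summary line screens nobody, and it adds no weight to the point about stage.

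**Conclusion.** The contradiction is real in the current text and should be fixed. If Appendix B is followed literally, the share of stage 0 patients enrolled is 0%, the enrolled population is narrower than that of H1 and H2, and the exclusion reasons in Appendix C are wrong for those women. If staff apply Section 10.0 from the record instead, none of this happens. The documents do not show which is done in practice.

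The harm is to the match between the stated and the enrolled population, and to the accuracy of the participant flow. It is not to the validity of the comparison between arms or to the planned size. The range of 6.7 to 8.6 months rests wholly on an assumed stage 0 share of 10% to 30% and should carry no weight in judging how serious the point is.

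**What to change.** Change the stage item in Appendix B so that it covers stages 0, 1 and 2, as Section 10.0 does. In the same amendment, reconcile the rest of the form with Section 10.0 line by line, including the English-language item and the documentation of physician clearance. Also state whether the form or Section 10.0 prevails for items read from the EMR.

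Review the screening records for stage 0 patients excluded on the basis of the form. Those still within 12 weeks of diagnosis can be re-screened. For the others, correct the exclusion reason in Appendix C so that the CONSORT counts are right.

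As a separate minor point, make the age in Section 1.0 (18+) agree with Sections 6.0 and 10.0 and the form (30-80).

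The cost is a small change to one form, one line in the summary, and a short check of the screening log. Sample size, randomization and analysis are unaffected.

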**Appendix C: Master list linking patients to Study ID and documenting study participation for CONSORT reporting**

Patient Last Name	Patient First Name	Date Assessed for Eligibility (mm/dd/yyyy)	Excluded? (Y/N)	If Excluded, reason (did not meet eligibility criteria, declined to participate, other)	Study ID (N/A for those excluded)	Random Assignment (Exercise Group, Control Group)
					1	
					2	
					3	
					4	
					5	
					6	
					7	
					8	
					9	
					10	
					etc.
